#### 4.1.2 Description and source of study population

See 1.4.3.

### 4.2 NUMBER OF PATIENTS

150 patients will be included in this trial.

### 4.3 PRESCREENING

A study coordinator will contact potentially eligible patients at the clinic or by phone, inform about the study and inquire about inclusion and exclusion criteria. A prescreening log including reason for being deemed eligible or not will be established. For patients who are on opioids and do not meet the leg pain intensity requirement of  $\geq 4$ , a new prescreening can be performed 24 hours after last opioid dose.

### 4.4 INCLUSION CRITERIA

All of the following conditions must apply to the prospective patient at screening prior to receiving study agent (e.g.):

- Age  $\geq 18$  years
- Radiating pain below the knee with a severity score of  $\geq 4$  on a 0-10 (NRS) in the previous 24 hours
- Signs of nerve root/spinal nerve involvement as indicated by at least one of the following features; myotomal weakness, dermatomal sensory disturbances (e.g. sensory loss, self-reported tingling/numbness), diminished reflexes, radiating pain exacerbation by SLR

### 4.5 EXCLUSION CRITERIA

Patients will be excluded from the study if they meet any of the following criteria:

- Not able to read or speak Norwegian.
- Unlikely to adhere to treatment and/ or complete follow-up (e.g ongoing serious psychiatric disease, drug abuse, plans to move)
- Sciatica of known cause other than disc herniation or degenerative stenosis.
- Neurogenic claudication, i.e. pain in the legs on walking or standing that resolves with sitting down or lumbar flexion.
- Symptoms indicating immediate surgery: cauda equina syndrome or a progressive large paresis.
- Women who attempt to conceive, are pregnant or breastfeeding.
- Previous episodes of asthma, urticaria or allergic-type reactions after taking aspirin or other NSAIDs.
- Active or history of peptic ulceration, gastrointestinal bleeding, or perforation.
- Use of drugs known to increase upper gastrointestinal adverse events in combination with Naproxen: anticoagulants, aspirin (acetyl salicylic acid), serotonin reuptake inhibitors and systemic corticosteroids.
- Hepatic enzyme (ASAT/ALAT) values above 1,5 x upper limit of normal (ULN)
- Renal function tests (creatinin/eGFR) outside normal range
- Congestive heart failure, established ischaemic heart disease, peripheral arterial disease, and/or cerebrovascular disease.

- Known hypersensitivity to Naproxen or any of the excipients (lactose, maize starch, povidone, sodium starch glycolate, talcum, magnesium stearate, polysorbate 80)
- Ongoing treatment with diuretics, ACE-inhibitors, lithium
- Scheduled for spinal surgery prior to the final study visit
- Reservation against intake of gelatine (the capsules contains gelatine, which among other things is produced by ingredients from pigs)

#### **4.6 RANDOMISATION AND ALLOCATION**

Study medicines will be packaged and labelled according to a pre-generated random number sequence; each sealed box will have a unique participant number. Computer-generated randomisation, stratified by center, will be used. Allocation to Naproxen or placebo will be at a 1:1 ratio.

### **5 TREATMENT**

#### **5.1 INVESTIGATIONAL MEDICINAL PRODUCTS (IMP).**

For this study oral Naproxen 500 mg tablets and placebo tablets are defined as IMP.

All IMPs will be encapsulated in Capsugel AAel-capsule. The placebo (vehicle without active drug) will consist of maize starch. Both the Naproxen and the placebo will be encapsulated, packaged and labelled by Kragerø Tablettproduksjon AS, in Kragerø, Norway. The appearance of the containers, labelling and the capsules will be identical for both treatment groups.

#### **5.2 RESCUE MEDICATION**

Paracetamol will be provided as rescue for unacceptable pain. Paracetamol can not substitute the study medication.

##### **5.2.1 Paracetamol (acetaminophen)**

At baseline the patients will receive a standard package of 100 tablets paracetamol 500 mg free of charge. The dosage will be 1-2 tablets as needed up to a maximum dose of 6 tablets in a 24 hours period. This is a standard dosing approved by The Norwegian Medicines Agency, see the Paracetamol SPC. Paracetamol (acetaminophen) is an established first-line therapy for mild to moderate pain [64]. It has shown analgesic activity in a variety of acute pain syndromes [65, 66] but has not been studied in sciatica. The incidence of adverse effects is low. Overdosing may cause hepatotoxicity but the risk of severe hepatotoxicity from therapeutic doses is considered extremely low [67] [68].

#### **5.3 OTHER PAIN MEDICATION**

Patients will be encouraged to avoid pain medication other than study and rescue medication. However, intake of other pain medication will not be classified as a protocol violation. Additional pain medication will be recorded daily by name and classified as (i) weak opioids, (ii) strong opioids or (iii) other and by DDD.

#### **5.4 STORAGE AND ADMINISTRATION**

The IMP and the rescue drugs will be stored and administered by collaborating pharmacies and handed out by the responsible pharmacist at the start of intervention. IMP capsules should be swallowed in whole and can be taken with or without food. Patients will be informed to keep the medicine in its original container, in a safe place out of reach of children. The rescue drugs used in this study have a marketing authorization in Norway, thus, the storage and preparation instructions will be according to the the package leaflets.

##### **5.4.1 IMP Dosage and Drug Administration**

The IMPs will be administered as fixed doses of 1 tablet (500 mg) twice daily, one tablet in the morning and one tablet in the evening. Thus, the first dose will be 500 mg.

##### **5.4.2 Duration of Therapy**

The duration of therapy is 10 days.

##### **5.4.3 Schedule Modifications**

There will be no modification of IMP dose or schedule.

### **5.5 CONCOMITANT MEDICATION**

All concomitant medication (incl. OTC drugs) used by the patient will be recorded in the patient's file. Patients will be encouraged not to take any of the following medication during the treatment phase of the study:

- Analgetics or NSAIDs, including over-the-counter (OTC) drugs
- Any new anti-depressant, including SSRIs, tranquilizer, sleep medication, neuroleptics, anti-epileptic drugs not on stable dose before start of the study
- Any of the following: aspirin, systemic corticosteroids, diuretics, ACE-inhibitors, lithium and anticoagulants

All new drugs taken during the study period (10 days) will be recorded in the CRF.

### **5.6 CONCOMITANT NON-PHARMACOLOGIC TREATMENTS**

No non-pharmacologic treatments for pain should be initiated during the trial (e.g., physical therapy, acupuncture).

### **5.7 SUBJECT COMPLIANCE**

Adherence to the medication schedule will be determined by daily self-report in the eCRF, and pill counts at the end of treatment. At day 2 a study nurse/physiotherapist will check the e-CRF for completeness and, if necessary, contact the patient in order to clear up misunderstandings or other issues that may impair compliance. Additionally, at the 5 day follow-up (by telephone) we will inquire about protocol adherence.

### **5.8 DRUG ACCOUNTABILITY**

Drug accountability of the IMPs and the rescue medication will primarily be assessed by pill counts of returned packages. Return, capsule count and destruction of the returned study drug will be administered by the collaborating pharmacies. Generally, pill counts are regarded as being more accurate than self-report or refill history [69]. In case of discrepancy between patients' diaries and pill count, the latter will be used.

### **5.9 DRUG LABELING**

The investigational product will have a label permanently affixed to the outside and will be labeled according with ICH GCP and national regulations, stating that the material is for clinical trial / investigational use only and should be kept out of reach of children. Labelling will be provided by Kragerø apotek including Study name, EudraCT Number, sponsor, center ID, name of PI, patient's initials and birthdate, enrolment code, date dispensed and name of prescribing doctor.

### **5.10 SUBJECT NUMBERING**

Each subject is identified in the study by a unique subject number that is assigned when subject signs the Informed Consent Form. Once assigned the subject number cannot be reused for any other subject.

## **6 STUDY PROCEDURES**

### **6.1 FLOW CHART**

Table 1. Trial flow chart

	Baseline	Start of treatment			Halfway follow-up		End of treatment	Final study visit	Withdrawal
Day	0	1	2	3-4	5 ( $\pm 1$ )	6-9	10	12 ( $\pm 2$ )	within 7 days after withdrawal
	Visit	Home	Home	Home	Home/ Telephone	Home	Home	Visit	Visit
Informed consent	X								
Inclusion/exclusion	X								
Medical history (including previous use of NSAIDs for sciatica)	X								
Treatment of current sciatica episode	X								
Physical examination*	X								
Vital signs (blood pressure, pulse)	X							X	X
Questionnaires:									
Leg pain intensity, back pain intensity	X, X†	X	X	X	X	X	X	X	X
Questionnaires:									
SBI, RMDQ-S	X				X		X	X	X

	Baseline	Start of treatment			Halfway follow-up		End of treatment	Final study visit	Withdrawal
Day	0	1	2	3-4	5 ( $\pm 1$ )	6-9	10	12 ( $\pm 2$ )	within 7 days after withdrawal
Questionnaire: GPC					X		X	X	X
Questionnaire: Work/study	X						X	X	X
Patient's guess regarding correct treatment								X	X
Self-report of IMD and rescue medication intake		X	X	X	X	X	X		
Protocol compliance, patient discontinuation			X		X			X	
Adverse events, self-report		X	X	X	X	X	X		
Adverse events, investigator					X			X	X
Laboratory tests† (safety)	X							X	X
Pregnancy test (women of childbearing potential)	X								
Return of pill boxes								X	X

\*SLR, sensory, muscular strength and reflex status of the lower extremities

†On day 0 patients will record back and leg pain both at the clinic and at home in the evening

‡Haemoglobin, hematocrit, leucocytes, thrombocytes, creatinin/eGFR, ASAT, ALAT, ALP

## 6.2 BY VISIT

### 6.2.1 Informed consent

Written informed consent will be obtained from all patients, with a copy to the included patients. See appendix B.

### 6.2.2 Washout

No specific washout procedure will be performed. However, at the day of inclusion patients will be encouraged to avoid analgetics/NSAIDs after bed time. Study medication will start the next morning.

### 6.2.3 Baseline

- The physiotherapist or physician decides on the inclusion/exclusion criteria and provides study ID.
- Medical history including disease history, corresponding treatment details and concomitant medication used within 28 days of treatment start.
- Clinical status including SLR, sensory, muscular strength and reflex status of the lower extremities, blood pressure and pulse. The clinical examination will be performed by a trained physiotherapist or physician.
- The patient receives log in details for Viedoc Me and completes the baseline questionnaires.
- The patient receives prescriptions and written information about study procedures, see appendix B. Women with childbearing potential will be advised to use a contraceptive during the 10 days of study.
- Study drugs are handed out by collaborating pharmacies.

### 6.2.4 During Treatment

During the treatment period patient reported outcomes will be recorded on a daily basis via the e-CRF. At day 2 a study nurse/physiotherapist will check the e-CRF for completeness, see 5.7. At day 5 ( $\pm 1$ ), there will be a follow-up, conducted by telephone.

### 6.2.5 Final Study Visit

At day 12 ( $\pm 2$ ) or within 7 days after withdrawal there will be a final study visit at the clinic. Patients will return all pill boxes for pill count. Questionnaires, vital signs, adverse events and laboratory tests will be performed.

### 6.2.6 Withdrawal Visit

Patients who withdraw or are withdrawn from the study will be encouraged to complete the final study visit.

## 6.3 CRITERIA FOR PATIENT DISCONTINUATION

Patients may be discontinued from study treatment and assessments at any time. The reason for discontinuation will be recorded. Specific reasons for discontinuing a patient for this study are:

- Voluntary discontinuation by the patient
- Safety reason as judged by the Principal Investigator
- Major protocol deviation
- Incorrect enrolment ie, the patient does not meet the required inclusion/exclusion criteria for the study
- Patient lost to follow-up
- A female patient becoming pregnant
- Patient's non-compliance to study treatment and/or procedures

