## 6.4 PROCEDURES FOR DISCONTINUATION

### 6.4.1 Patient Discontinuation

The patient is not obliged to give his or her reasons for withdrawing prematurely from the trial. However, a reasonable effort will be made to ascertain the reason, while fully respecting the patient's rights. If he or she is unwilling or unable to complete of the final study visit he or she will be invited to report safety and efficacy endpoints either in the eCRF or by phone. Special consideration will be given to collect remaining medication and pill boxes. If the withdrawal is exclusively related to the trial drug therapy, this will be classified as a violation of the protocol and the data collection will be continued as specified in 6.2.4 and 6.2.5. Patient discontinuation will be monitored by checking the eCRF at day 2 and at the telephone follow-up at day 5 ( $\pm 1$ ).

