# **9 STATISTICAL METHODS AND DATA ANALYSIS**

## **9.1 DETERMINATION OF SAMPLE SIZE**

The sample size calculation is based on a mean difference between the Naproxen group and the placebo group of 1.5 (0-10) at ten days with a SD of 2.5 using a two-sample t test. There is no robust evidence for the smallest worthwhile

between group pain relieving effect in sciatica. In previous sciatica studies sample size were calculated based on between group differences of 1.5 and 1.0 [80, 81]. In a recent RCT of pregabalin the sample size was calculated based on a between group difference of 1.5 [36]. In knee osteoarthritis, a condition in which NSAIDs are generally recommended, the treatment effect of NSAIDs is about 1.0 [82-84]. The estimated SD of 2,5 is based on a recent Cochrane review of NSAID studies in sciatica [30].

Assuming 90% power and a two-tailed 5% significance level a sample size of 60 subjects is needed in each treatment arm. Allowing for a combined dropout and non-compliance rate  $\leq 20\%$  [85] the total number of subjects will be 150.

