19.1 Adherence

The prescribed doses of study medication is one tablet twice daily for ten days, i.e. a total of 20 tablets. Adherence is assessed by the percentage of prescribed doses taken, measured by pill count if the bottle is returned. If the bottle is not

returned adherence will be based on self-report. Each day patients are asked to record study medication intake and give the reason if not taking the prescribed amount. Reasons for non-adherence will be reported based on patients' free-form text comments in the diaries, and investigators' comments in the case report forms (CRFs). This information will also be used in subsequent classification of potential missing data as being "missing not at random" (MNAR), "missing at random" (MAR) or "missing completely at random" (MCAR) [1].

19.2 *Protocol deviations*

Important (major) protocol deviations will be reported by the number of subjects who

- entered into the study not meeting the entry criteria
- developed withdrawal criteria during the study but were not withdrawn
- received the wrong study treatment or incorrect dose
- had less than 80% intervention adherence

Not important (minor) protocol deviations will be reported by the number of subjects who

- received drugs that they were encouraged to avoid during study, i.e. analgesics, NSAIDs, anti-depressants, tranquilizers, sleep medications, neuroleptics and anti-epileptic drugs, if not on a stable dose prior to enrollment.
- received drugs which would have excluded them from participating in the trial, i.e. anticoagulants, aspirin, serotonin reuptake inhibitors, systemic corticosteroids, diuretics, ACE-inhibitors and lithium.

20 Analysis populations

There will be 3 analysis populations:

1. The intention-to-treat (ITT) population, including all randomized subjects.
2. The per protocol (PP) population, including subjects without any important protocol deviations.
3. The safety population, including subjects who received at least one dose of study medication and who had at least one subsequent safety-related observation.

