28.1 Measures to minimize the amount of missing data

- To facilitate simple access and timely responses patients receive daily text message reminders with a link to the electronic diary. A paper CRF is provided as back-up in case the eCRF is unavailable.
- To ensure clear and concise wording, and response alternatives, only validated patient reported outcomes, appropriate for sciatica, are used.
- To reduce unnecessary response burden the number of outcomes are limited.
- To ensure data completeness study staff checks the e-CRF at day 2 and day 5, and if necessary contacts the patient to clear up issues that may impair compliance.
- To preserve the ITT population data will be continued to be collected after withdrawal. Reasons for withdrawal are pre-specified.

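### Protocol 6.3 lets assessments end together with study drug, and Protocol 6.4.1 secures later daily scores only for purely drug-related withdrawals, although SAP 28.1 and the ITT analysis count on them

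*Protocol*

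**What the plan says.** **Stopping.** Protocol 6.3 treats treatment and follow-up as one thing: "Patients may be discontinued from study treatment and assessments at any time". The specific reasons it lists include major deviation, incorrect enrolment, and non-compliance with treatment or procedures.

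**Data after stopping.** Protocol 6.4.1 makes one clear provision for continued daily recording. If the withdrawal concerns the trial drug and nothing else, "this will be classified as a violation of the protocol and the data collection will be continued", with reference to the daily eCRF entries (6.2.4) and the final visit (6.2.5). For everyone else, Protocol 6.2.6 encourages attendance at a final visit. Those who will not or cannot attend are invited under 6.4.1 to report endpoints by eCRF or telephone.

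**SAP.** Section 28.1 gives an unqualified assurance: "To preserve the ITT population data will be continued to be collected after withdrawal". Section 19.2 lists among the important deviations subjects who "developed withdrawal criteria during the study but were not withdrawn", and separately those with under 80% adherence. Section 20 removes anyone with an important deviation from the per-protocol (PP) set. The ITT population is all randomised subjects (SAP 20), whatever their adherence (Protocol 9.3).

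**The concern.** The primary analysis needs a leg-pain score from every randomised patient on each day to day 10. The protocol permits those scores to stop for reasons, such as non-compliance, that can themselves reflect poor pain relief or side effects. Under an ITT aim, stopping capsules is something to observe through, not a reason to stop measuring.

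Where measurement does stop, the primary model fills the gap by assuming the data are missing at random (SAP 28.3). The sensitivity analyses in SAP 27.5 are a PP repeat, multiple imputation and added covariates. Imputation is described only under missing at random or missing completely at random. SAP 28.2 and 29.2 say that further analyses may be done, but none that allows for data missing not at random is specified. Collecting the scores is therefore the main protection, and Protocol 6.3 weakens it.

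**Working it through.** **1. Which withdrawals are covered?**

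- *Drug only:* Protocol 6.4.1 secures daily entries and the final visit. No gap.
- *Major deviation, incorrect enrolment, or non-compliance not confined to the drug:* Protocol 6.3 permits assessments to end. Protocol 6.2.6 and 6.4.1 offer a final visit or a remote report, but no daily entries. SAP 28.1 assumes collection goes on. This is the gap.

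**2. Does the final visit replace the missing diary days?** Protocol 6.2.5 places it within 7 days after withdrawal. For withdrawal on day *w* the latest day is *w* + 7. For *w* = 2 that is day 9, before the day-10 endpoint. The diary days not recorded number 10 − *w*: 8 of 10 for *w* = 2, and 5 of 10 for *w* = 5. The flow chart gives one leg-pain rating at the withdrawal visit. The SAP does not say how that rating enters a model with 11 daily time points (SAP 27.1).

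**3. The deviation rules are circular.** Under 80% adherence is an important deviation (SAP 19.2). A major deviation is a reason to discontinue (Protocol 6.3). Not withdrawing a patient who meets a withdrawal criterion is a further important deviation (SAP 19.2).

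**4. Is this a power problem?** The inputs are in Protocol 9.1 and 4.6: a difference "of 1.5 (0-10) at ten days with a SD of 2.5 using a two-sample t test"; 90% power at a two-sided 5% level, giving 60 per arm; an allowance of up to 20% for dropout and non-compliance together; and "Allocation to Naproxen or placebo will be at a 1:1 ratio".

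- Standardised difference = 1.5 / 2.5 = 0.6.
- The two-sample t test at two-sided 5% and 90% power gives 59.35, rounded up to 60 per arm. The plan's figure reproduces.
- 120 / (1 − 0.20) = 150, or 75 per arm. This reproduces too.

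Power by loss, with the 1.5-point effect unchanged:

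| Loss | Observed per arm | Power |
|---|---|---|
| 0% | 75 | 0.9545 |
| 10% | 67.5 | 0.9333 |
| 20% | 60 | 0.9031 |
| 30% | 52.5 | 0.8611 |

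Loss within the planned allowance keeps about 90% power. The issue is bias, not precision.

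**5. How might bias scale?** The documents give no input for this, so what follows is an assumption shown over a range. Suppose a share *f* of the naproxen arm stops the drug and has no benefit at day 10. The effect over all randomised patients is then 1.5 × (1 − *f*):

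| *f* | Effect in all randomised | Gap from 1.5 |
|---|---|---|
| 5% | 1.425 | 0.075 |
| 10% | 1.35 | 0.15 |
| 15% | 1.275 | 0.225 |
| 20% | 1.20 | 0.30 |

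If those later scores are absent, a missing-at-random analysis could lean toward 1.5, so the last column is the most it could overstate the effect in this scenario. Scores recorded before withdrawal stay in the model and would reduce the gap. Patients already covered by 6.4.1 would not contribute to it.

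**The case against.** The best defence is that a site can comply with everything. Protocol 6.3 says *may*, so ending assessments is permitted, not required. A site can withdraw the patient, which satisfies SAP 19.2, and keep collecting data, which satisfies SAP 28.1. The patient who stops capsules purely because of side effects or lack of relief is already protected by 6.4.1. The flow chart has a withdrawal visit with the main questionnaires. Adherence by pill count is known only when boxes come back at the final visit, after the day-10 score is due, and the checks on days 2 and 5 are meant to solve problems, not to trigger withdrawal. A patient who has stopped filling in diaries will not resume because the wording changed.

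Much of this stands. A reader might infer that the rules cannot all be followed; the documents do not support that, because the permissive wording leaves a consistent route open. A reader might also infer that the SAP penalises sites that keep such patients in. It does not: SAP 19.2 counts subjects, the only consequence is leaving the PP set used for a sensitivity analysis, and ITT membership is untouched.

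What the defence does not remove is that the consistent route is nowhere required. A site that follows Protocol 6.3 as written may end the diary for a patient withdrawn for a major deviation or incorrect enrolment, and nothing in 6.2.6 or 6.4.1 tells it to continue.

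**Conclusion.** The point holds in a limited form. For withdrawals not exclusively drug-related, SAP 28.1 promises data that the protocol permits sites to stop collecting and does not otherwise secure. The loss would fall on daily primary-outcome scores in an ITT analysis that then relies on missing at random, with no specified analysis under another assumption. SAP 19.2 adds ambiguity, not a sanction.

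The size of any bias cannot be derived from the documents. They do not split the 20% allowance between dropout and non-compliance, do not say how many withdrawals would fall outside 6.4.1, and give no off-treatment pain scores. The 0.075 to 0.30 range above rests on an assumed one-arm loss with no residual benefit; similar losses in both arms would partly cancel. It is tempting to take half the allowance as lost patients, 15 of 150, and a 2-point shift in 10% of one arm as a 0.2-point bias. Neither input is in the documents, and the 15 patients span both arms while the shift is applied to one.

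The sample size is sound on its stated inputs and needs no change. The wording should be reconciled because the data at risk are avoidable losses.

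**What to change.** Reconcile Protocol 6.3, 6.2.6 and 6.4.1 with SAP 19.2 and 28.1 by treating the end of study drug and the end of data collection as two separate events:

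- **Protocol 6.3, 6.2.6 and 6.4.1:** state that, whatever the reason for stopping study drug, daily diaries to day 10 and the final visit continue unless the patient declines further follow-up. Merely deleting *exclusively* from 6.4.1 would not do, because it would leave the patient's right to decline unstated in that rule.
- **SAP 19.2:** reword the item on patients who met withdrawal criteria so that continued follow-up is not itself a deviation.
- **SAP 28.1:** keep the stated intent and point it to the amended protocol sections.

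The existing reasons for stopping study drug are left unchanged, and no clinical stopping rule is proposed. The cost is wording in both documents, with the protocol change handled as an amendment under Protocol 10.3. The diary, the text reminders and the telephone contact already exist, so no new data system is needed.
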